Appendix 6. Medical Research Council (MRC) Scale for Muscle Strength Testing

The following muscle groups will be evaluated using the MRC Scale:

Muscle Group	MRC Scale Score					
	0	1	2	3	4	5
Right upper arm abduction						
Left upper arm abduction						
Right elbow flexion						
Left elbow flexion						
Right wrist extension						
Left wrist extension						
Right wrist flexion						
Left wrist flexion						
Right index finger abduction						
Left index finger abduction						
Right thumb abduction						
Left thumb abduction						
Right knee extension						
Left knee extension						
Right foot dorsal flexion						
Left foot dorsal flexion						
Right foot plantar flexion						
Left foot plantar flexion						
Total score (90)						

- 0 - No contraction
- 1 - Flicker or trace contraction
- 2 - Active movement, with gravity eliminated
- 3 - Active movement against gravity
- 4 - Active movement against gravity and resistance
- 5 - Normal power

Evaluation will proceed using the following algorithm:

### General Guidelines

1. For each muscle tested, the examiner stands to the side being tested, and the subject is sitting upright and positioned to allow full movement of the joint against gravity.
2. The examiner demonstrates the desired movement against gravity. The examiner then requests the subject to repeat the motion.
3. If the subject can move through the desired range of motion against gravity, the examiner attempts to apply resistance in the testing position while stating *"Hold it, don't let me push it down" or "Hold it, don't let me bend it"*
4. If the subject tolerates no resistance, the muscle score is Grade 3. If the subject tolerates some resistance, the score is Grade 4, and full resistance, Grade 5.
5. If the subject cannot move against gravity, the subject is repositioned to allow movement of the extremity with gravity eliminated. If supporting the limb, the examiner provides neither assistance nor resistance to the subject's voluntary movement. This gravity-eliminated positioning will vary for each muscle tested. If the subject cannot complete at least partial range of motion with gravity eliminated, the muscle or tendon is observed and/or palpated for contraction.
6. For a bedridden subject who cannot sit up in a bed placed in the chair position or on the edge of the bed, alternate positions for testing the lower extremity are included in this protocol.

### Upper Arm (shoulder) Abduction

- Testing position - arm out from the side at shoulder level
- The examiner demonstrates the motion, then states *"Lift your arm out to the side to shoulder level."* The hand giving resistance is contoured over the subject's arm just above the elbow. The other hand stabilizes the shoulder above the shoulder joint. The examiner states *"Hold it,*

---

*don't let me push it down.*" To assess grades 3, 4, or 5, please see General Guidelines, section 4 above.

[figure not shown]
- If weaker than Grade 3, the subject lies supine with arms at the side. The examiner supports the arm just above the elbow and at the wrist to assure that the shoulder does not externally rotate (turn outward). The subject attempts to move the arm out to the side. The examiner states: *"Try to move your arm out to the side"*. Grade 2 is assigned if the subject moves with gravity eliminated.
- If weaker than Grade 2, the examiner states *"Try to move your arm out to the side"* and palpates the middle deltoid muscle for contraction, and scores as Grade 1 or 0 as previously defined.

### **Elbow Flexion**

- Test position - forearm supinated and flexed slightly more than 90 degrees.
- Verbal instructions: *"Bend your elbow slightly more than 90 degrees"*. The hand giving resistance is contoured over the flexor surface of the forearm proximal to the wrist. The examiner's other hand applies counterforce by cupping the palm over the anterior superior aspect of the shoulder. The examiner then states: *"Hold it. Don't let me push it down"* and scores Grades 3, 4, or 5 as previously described.
- If weaker than Grade 3, the shoulder is abducted to 90 degrees. The examiner supports the arm under the elbow and, if necessary, the wrist as well. The forearm is turned with the thumb facing the ceiling. With the elbow extended, the subject attempts to flex the elbow. The examiner states: *"Try to bend your elbow."* Grade 2 is assigned if the subject can flex the elbow.
- If weaker than Grade 2, the forearm is supinated and positioned at the side in approximately 45 degrees of elbow flexion. The examiner states *"Try to bend your elbow"*, palpates the biceps tendon and scores as either Grade 1 or 0.

### **Wrist Extension**

[figure not shown]
- Test position - arm at the side, elbow flexed to 90 degrees with the forearm pronated and the wrist fully extended.
- Verbal instructions: *"Bend your wrist up as far as possible."* The examiner's hand giving resistance is placed over the back of the subject's hand just distal to the wrist. The examiner's other hand supports the subject's forearm. The examiner then states: *"Hold it. Don't let me push it down"* and scores Grades 3, 4 or 5.
- If weaker than Grade 3, the elbow is flexed to 90 degrees and forearm turned with thumb facing the ceiling. The forearm and wrist are supported by the examiner. The examiner states: *"Bend your hand toward me"*. Grade 2 is assigned if the subject can extend the wrist.
- If weaker than Grade 2, the examiner states *"Bend your wrist toward me"* and palpates the two extensor tendons, one on each side of the wrist and scores as Grade 1 or 0. The examiner is careful not to palpate the tendons in the middle of the wrist.

---

## Wrist Flexion

- Test position - arm at the side, elbow flexed to 90 degrees with the forearm supinated and the wrist fully extended.
- Verbal instructions: "*Bend your wrist up as far as possible.*" The examiner's hand giving resistance is placed on the palm of the subject's hand just distal to the wrist. The examiner's other hand supports the subject's forearm. The examiner then states: "*Hold it. Don't let me push it down*" and scores Grades 3, 4 or 5.
- If weaker than Grade 3, the forearm and wrist are supported by the examiner. The examiner states: "*Bend your hand toward me*". Grade 2 is assigned if the subject can flex the wrist.
- If weaker than Grade 2, the examiner states "*Bend your wrist toward me*" and palpates the flexor tendons and scores as Grade 1 or 0.
- 

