### Knee Extension

- Test position - sitting upright with the knee fully extended to 0 degrees. Avoid knee hyperextension.
- Verbal instructions; "*Straighten your knee*". The hand giving resistance is contoured on top of the leg just proximal to the ankle. The other hand is placed under the thigh above the knee. The examiner then states "*Hold it. Don't let me bend it*" and scores Grades 3, 4 or 5.
- If weaker than Grade 3, the subject lays on the non-testing side. The examiner stands behind the subject at knee level. The leg not being tested may be flexed for stability. One arm cradles the leg being tested around the thigh with the hand supporting the underside of the knee. The other hand holds the leg just above the ankle. The examiner states: "*Straighten your knee.*" Grade 2 is assigned if the subject can extend the knee (Figure 3).
- If weaker than Grade 2, the subject is supine and the examiner states: "*Push the back of your knee down*" or "*Tighten your knee cap*" and palpates the quadriceps tendon, and scores as Grade 1 or 0.

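### Appendix 6 gives the MRC wrist-flexion test a position that conflicts with its own command, so 2 of 18 items may be graded inconsistently (minor)

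*Combined protocol and SAP*

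**What the plan says.** Appendix 6, Wrist Flexion, places the arm at the side with the "elbow flexed to 90 degrees with the forearm supinated and the wrist fully extended". The command is "Bend your wrist up as far as possible", and the resisting hand "is placed on the palm of the subject's hand just distal to the wrist". For a subject weaker than Grade 3, the examiner supports the forearm and wrist and asks for the hand to be brought toward the examiner; "Grade 2 is assigned if the subject can flex the wrist". Below that, the flexor tendons are palpated for Grade 1 or 0.

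The neighbouring item, Wrist Extension, uses "elbow flexed to 90 degrees with the forearm pronated and the wrist fully extended". Its lower-grade commands are the same as those for flexion, but it also specifies a thumb-up forearm for Grade 2.

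The General Guidelines of Appendix 6 put the examiner at the side being tested (item 1). They have the subject repeat a demonstrated movement against gravity (item 2), after which "the examiner attempts to apply resistance in the testing position" (item 3). A subject who cannot move against gravity is repositioned to remove gravity, in a position that varies by muscle (item 5).

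Section 6.2 names MRC strength among the secondary measures. Section 4.2.8 schedules it on Day 0, Day 30, Day 60, Day 90, and at 6 and 9 months.

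**The concern.** If the test position is where resistance is applied, full extension is the wrong end of range for a flexion test. One examiner may follow the position line and another the command, and they would not be grading the same thing. The lower-grade step has a separate weakness: a subject with the thumb up who obeys the command may extend the wrist, while the criterion asks whether the wrist can be flexed.

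Flexor carpi ulnaris and flexor carpi radialis are two of the ten muscles injected on each side (Tables 1 and 2), and wrist flexion is the only MRC item that covers them. Dynamometry (section 4.2.10) measures pinch, grip and lower leg extension, so no other test in the plan measures wrist flexion directly. At stake is the consistency of that item between examiners and between visits.

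**Working it through.** **1. Reproduce the stated total.** Appendix 6 lists 9 movements on 2 sides: 9 × 2 = 18 items. With a top grade of 5, 18 × 5 = 90, which matches the total printed in the table.

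**2. Compare the position line across the nine movements.**
- Five give a position reached by the tested movement: upper arm abduction (arm at shoulder level), elbow flexion (slightly past a right angle), wrist extension (extended), knee extension ("sitting upright with the knee fully extended to 0 degrees") and foot dorsiflexion (dorsiflexed).
- Two give only a set-up posture: index finger abduction and thumb abduction, neither of which names the abducted position.
- Two give the end of the opposite movement: wrist flexion (extended) and foot plantarflexion (dorsiflexed).

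Appendix 6 therefore uses the term in more than one sense and never says which applies. Under item 3 of the General Guidelines, the wrist-flexion line conflicts with its command. Read as a starting posture, it does not.

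**3. Check the lower-grade commands.** The examiner stands at the tested side. With the thumb up, the palm faces the midline, so extension carries the hand toward the examiner and flexion carries it away. In that posture the command suits the extension item and not the flexion item. The flexion item gives no forearm position for this step. If the forearm stays supinated, flexion is still against gravity, contrary to item 5. If it is turned thumb-up, the command points the wrong way.

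**4. Extent.**
- Items: 2 of 18 = 11.1%.
- Points carried by those items: 2 × 5 = 10 of 90 = 11.1%. This is a ceiling, not an estimate of error.
- Item scores with complete data: 18 subjects × 6 assessments × 2 items = 216, of 18 × 6 × 18 = 1,944.

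**5. Possible shift in the total.** The documents give no misgrading rate or size, so this is an assumption. At 1 grade per item, 2 × 1 = 2 points (2/90 = 2.2%). At 2 grades per item, 2 × 2 = 4 points (4/90 = 4.4%). Two grades is the full span of the resisted step (Grades 3 to 5).

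**6. The parallel item.** Foot Plantarflexion starts from full dorsiflexion, as Foot Dorsiflexion does, and scores Grade 1 or 0 by palpating the tibialis anterior tendon, the same tendon used for dorsiflexion. Counting it as well gives 4 of 18 items (22.2%), carrying at most 20 of 90 points.

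**The case against.** Most of the wrist-flexion item does describe a flexion test. The command, the resistance on the palm, the Grade 2 criterion and the palpation of flexor tendons all target flexion. Under items 2 to 4 of the General Guidelines the subject must first show active movement against gravity, so an examiner has watched flexion before applying resistance. The two abduction items show that a test position can be a set-up posture, and on that usage extending first and then bending up is coherent. All of this stands, and it makes the text ambiguous rather than plainly wrong.

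A reader might infer more: that the item yields false Grade 5 scores, because an already extended wrist cannot be pushed further, and so biases results toward preserved strength. The documents do not support that. It would require the examiner, having just seen active flexion, to return the wrist to full extension and resist there. A reader might also conclude that the line was carried over from the extension item. The near-identical wording suggests this but does not show it.

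It can also be said that a reading applied the same way throughout would largely cancel in change from baseline. That is fair for a constant shift. It does not help if examiners differ or if a reading produces a ceiling, and Appendix 6, unlike Appendix 7 for circumference, does not ask for the same assessor each time.

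The objection leaves two things unanswered: item 3 of the General Guidelines still ties resistance to the test position, and the lower-grade commands can still elicit the wrong movement.

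**Conclusion.** The point holds as a minor inconsistency in an operative scoring instruction. Grading may be inconsistent on 2 of 18 items at the six MRC assessments; Screening and Days 7, 14 and 21 have no MRC testing and are unaffected. The 2 to 4 point shift in the total rests on the assumed 1 to 2 grades per item in the same direction on both sides. It is illustrative, and neither its frequency nor its direction can be derived from the documents.

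The consequence is limited. MRC strength is a secondary, descriptive measure, section 6 rules out hypothesis testing on any endpoint, and the safety objective is untouched. The correction is still worth making, because this is the only MRC item for two injected muscles.

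**What to change.** In Appendix 6, Wrist Flexion:
- give the hold position as wrist fully flexed, or say that the extended position is only the start and that resistance is applied after the wrist has been flexed;
- state the forearm position for gravity-eliminated testing;
- replace the commands for the weaker grades with ones that name wrist flexion.

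In Foot Plantarflexion, correct the position in the same way, and replace the tibialis anterior tendon with a plantarflexor structure for Grade 1 or 0.

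In the General Guidelines, add a sentence saying whether test position means the start or the hold, so that all nine movements are read alike.

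The cost is a few wording changes and a note to examiners. No test, visit or subject is added, and the 18 items and the maximum of 90 do not change. If assessments have already been done, ask the examiners which position they used and record the answer with the data.

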## Index finger abduction

- Test position - arm at the side, elbow flexed to 90 degrees, fingers extended, with the wrist in the midposition between supination and pronation.
- Verbal instructions: "*Spread your fingers apart.*" The examiner's finger giving resistance to the superior portion of the tip of the index finger. The examiner then states: "*Hold it. Don't let me push it down*" and scores Grades 3, 4 or 5.
- If weaker than Grade 3, the forearm and wrist are pronated and the hand is placed on a flat surface. The examiner states: "*Spread your fingers apart*". Grade 2 is assigned if the subject can abduct the index finger.
- If weaker than Grade 2, the examiner states "*Spread your fingers apart*" and palpates the FDI muscle belly and scores as Grade 1 or 0.

## Thumb abduction

- Test position - arm at the side, elbow flexed to 90 degrees, forearm supinated and supported on a flat surface, with the wrist and fingers extended.
- Verbal instructions: "*Raise your thumb straight up*" such that the thumb moves in a plane that is at a right angle to the palmar surface. The examiner's finger gives resistance to the superior portion of the thumb. The examiner then states: "*Hold it. Don't let me push it down*" and scores Grades 3, 4 or 5.
- If weaker than Grade 3, the forearm and wrist are placed in midposition between supination and pronation. The examiner then states: "*Move your thumb inward*" such that the thumb moves in a plane that is at a right angle to the palmar surface. Grade 2 is assigned if the subject can abduct the thumb.
- If weaker than Grade 2, the examiner states "*Move your thumb inward*" and palpates the APB muscle belly and scores as Grade 1 or 0.

[figure not shown]
---

### Knee Extension

- Test position - sitting upright with the knee fully extended to 0 degrees. Avoid knee hyperextension.
- Verbal instructions; "*Straighten your knee*". The hand giving resistance is contoured on top of the leg just proximal to the ankle. The other hand is placed under the thigh above the knee. The examiner then states "*Hold it. Don't let me bend it*" and scores Grades 3, 4 or 5.
- If weaker than Grade 3, the subject lays on the non-testing side. The examiner stands behind the subject at knee level. The leg not being tested may be flexed for stability. One arm cradles the leg being tested around the thigh with the hand supporting the underside of the knee. The other hand holds the leg just above the ankle. The examiner states: "*Straighten your knee.*" Grade 2 is assigned if the subject can extend the knee (Figure 3).
- If weaker than Grade 2, the subject is supine and the examiner states: "*Push the back of your knee down*" or "*Tighten your knee cap*" and palpates the quadriceps tendon, and scores as Grade 1 or 0.

### Foot Dorsiflexion

- Test position - sitting, with the heel on floor, foot in full dorsiflexion, and shoes and socks removed.
- Verbal instructions: "*Bend your foot up as far as possible.*" The toes are relaxed during the test. The hand giving resistance is cupped over the top of the foot proximal to the toes. The other hand is contoured around the front of the leg just proximal to the ankle. The examiner then states "*Hold it, don't let me push it down*" and scores Grade 3, 4 or 5.
- If weaker than Grade 3, but there is partial range of motion against gravity, assign Grade 2.
- If weaker than Grade 2, palpate the tibialis anterior tendon, and score as Grade 1 or 0.
- The bedridden subject is tested supine, with the leg extended and a pillow placed under the knee.

### Foot Plantarflexion

- Test position - sitting, with the heel on floor, foot in full dorsiflexion, and shoes and socks removed.
- Verbal instructions: "*Lift your heel and point your toes down as far as possible.*" The hand giving resistance is cupped over the top of the foot proximal to the ankle. The other hand is contoured around the front of the leg just proximal to the ankle. The examiner then states "*Hold it, don't let me push it down*" and scores Grade 3, 4 or 5.
- If weaker than Grade 3, but there is partial range of motion against gravity, assign Grade 2.
- If weaker than Grade 2, palpate the tibialis anterior tendon, and score as Grade 1 or 0.
- The bedridden subject is tested supine, with the leg extended and a pillow placed under the knee.

---

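### The MRC plantarflexion test in Appendix 6 separates Grade 1 from Grade 0 by palpating the opposing muscle, so the only gastrocnemius item can be misgraded by up to 2 of 90 points

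*Combined protocol and SAP*

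**What the plan says.** Section 6.2 names MRC muscle strength among the secondary endpoints. Section 4.2.8 says the scale is for the injected muscle groups and refers to Appendix 6 for the method. Appendix 6 lists nine movements, each scored 0 to 5 on the right and left.

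The General Guidelines (item 5) set the rule for the lowest grades: if there is not even partial movement with gravity eliminated, "the muscle or tendon is observed and/or palpated for contraction". Each movement then has its own line. Knee extension "palpates the quadriceps tendon, and scores as Grade 1 or 0" and wrist flexion "palpates the flexor tendons and scores as Grade 1 or 0".

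For foot plantarflexion the instruction to the subject is "Lift your heel and point your toes down as far as possible". The line for the lowest grades is "If weaker than Grade 2, palpate the tibialis anterior tendon, and score as Grade 1 or 0". Foot Dorsiflexion, the test of the opposite movement, contains the identical sentence.

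The stated position for plantarflexion, also shared with the dorsiflexion test, is "Test position - sitting, with the heel on floor, foot in full dorsiflexion, and shoes and socks removed".

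**The concern.** One tendon cannot be the right place to feel for a contraction in two opposed movements. Appendix 6 itself uses the tibialis anterior for dorsiflexion, so the plantarflexion line looks like text carried over from the preceding test and not adapted.

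The error can go either way. A trace calf contraction that is not felt at the front of the leg gives a false 0. Activity in the tibialis anterior gives a false 1. The tibialis anterior is itself an injected muscle, so a false 1 would also credit one treated muscle to another.

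The gastrocnemius receives 48 of the 256 injections (Tables 1 and 2), and plantarflexion is the only MRC movement that corresponds to it. No other strength measure covers it: dynamometry (section 4.2.10) takes pinch, grip and lower leg extension. Calf circumference is measured, but that is size, not contraction.

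**Working it through.** **Inputs.** Nine movements, two sides and a printed total of 90 (Appendix 6); grades 0 to 5 and six assessment times, namely Day 0, 30, 60, 90 and 6 and 9 months (section 4.2.8); 18 subjects (section 3.3).

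**The plan's own total.** 9 movements × 2 sides × 5 = 90. This reproduces the printed figure.

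**Palpated structure by movement (Appendix 6).**

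| Movement | Palpated for Grade 1 or 0 | Muscle under test? |
|---|---|---|
| Upper arm abduction | middle deltoid | yes |
| Elbow flexion | biceps tendon | yes |
| Wrist extension | wrist extensor tendons | yes |
| Wrist flexion | wrist flexor tendons | yes |
| Index finger abduction | FDI | yes |
| Thumb abduction | APB | yes |
| Knee extension | quadriceps tendon | yes |
| Foot dorsiflexion | tibialis anterior tendon | yes |
| Foot plantarflexion | tibialis anterior tendon | **no** |

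Eight of nine follow the same rule, and plantarflexion alone departs from it.

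**Bound on the palpation error.** The step only separates Grade 0 from Grade 1.
- Per side: 1 − 0 = 1 point. Both sides: 2 points.
- Share of the total: 2/90 = 2.2%.
- Share of the plantarflexion points: 2/(2 × 5) = 2/10 = 20%.
- Plantarflexion gradings planned: 18 × 2 × 6 = 216.

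**Effect on the mean total at one visit, 18 subjects assessed.** One misgraded side moves the mean by 1/18 = 0.056 points. If a share p of the 36 sides is below Grade 2 and all are misgraded in the same direction, the shift is 36p/18 = 2p. The documents do not give p, so these shares are assumptions:

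| Assumed p | Largest shift in mean total (points) |
|---|---|
| 5% | 0.1 |
| 20% | 0.4 |
| 50% | 1.0 |
| 100% | 2.0 |

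**What is unclear but not shown to be wrong.** Full dorsiflexion may be only the starting position. Wrist flexion likewise starts from the opposite end of its range: "elbow flexed to 90 degrees with the forearm supinated and the wrist fully extended". But item 3 of the General Guidelines says "the examiner attempts to apply resistance in the testing position", which would put the resistance where the foot is still dorsiflexed. The resisting hand moves from near the toes in the dorsiflexion test to above the ankle here, where the second hand also goes. The spoken command, to resist a downward push, can oppose a lifted heel; with the foot held in dorsiflexion it does not oppose plantarflexion. The text does not say which is meant.

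Two conditional figures follow. If raters resist dorsiflexion but grade the movement step correctly, Grades 3 to 5 are affected: 2 points × 2 sides = 4, and 4/90 = 4.4%. If they score the whole item as dorsiflexion: 5 × 2 = 10, and 10/90 = 11.1%.

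**The case against.** The strongest reply is that this is a drafting slip with little consequence. Palpation is reached only below Grade 2, MRC strength is one of several descriptive secondary measures, section 6 rules out hypothesis testing on any endpoint, and the primary endpoint is safety. All of that stands, and it limits the weight of the point.

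It can also be said that the general rule and the clear instruction to point the toes down give a rater reason to feel the calf anyway. Some raters would. But the specific line names a tendon and the general rule does not, so grading would depend on which instruction each rater follows, without any record of it.

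The objection to the arithmetic is partly right. The 2p shifts need every affected side misgraded in one direction, whereas the errors can go both ways and partly cancel. The 0.056 holds for full attendance. Section 3.5.2 foresees discontinuations, and with 12 subjects assessed, as an example, one side would move the mean by 1/12 = 0.083.

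The 4.4% and 11.1% figures can be challenged because they depend on readings the text does not force, and the 11.1% case requires raters to disregard the spoken instruction. They do not form part of the established effect.

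**Conclusion.** The point holds. The Grade 1 or 0 rule for plantarflexion names the wrong muscle, and no other part of the document corrects it. Apart from the documents' own use of the tibialis anterior for dorsiflexion, the conclusion rests only on the basic anatomy that this muscle opposes plantarflexion.

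The established size is at most 2 of 90 points per assessment, confined to sides below Grade 2. How often that occurs cannot be read from the documents. Section 1.8 expects progressive weakness in all limbs, so low grades may become more common during the 9 months. The position and resistance wording is ambiguous and worth clarifying, but is not shown to be wrong.

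The correction should be made because the rule is operative and the change costs almost nothing. The study's main conclusions do not depend on it.

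**What to change.** In Appendix 6, Foot Plantarflexion:

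1. Change the palpation site to the gastrocnemius or Achilles tendon.
2. State the position in which resistance is applied, and word the hand placement and spoken command so that they clearly oppose plantarflexion.
3. Brief the raters, and flag plantarflexion scores already taken. Start with Grades 0 and 1, the only grades the palpation step decides.

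A minor, separate item can be settled in the same edit: both foot tests give Grade 2 for partial range against gravity, whereas section 4.2.8 and item 5 of the General Guidelines tie Grade 2 to movement with gravity eliminated. Reconcile these, or say that the foot is a deliberate exception.

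The cost is appendix wording and a short rater briefing. No assessment or visit is added, and the total stays at 90. With the palpation line corrected, the possible misgrade from this step falls from 2 points to 0.
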